## **8.8. Pharmacodynamic (PD) Analyses**

Plasma samples will be collected for measurement of VAP-1/SSAO activity and methylamine levels according to the schedule of activities in Section 1.3 of the protocol.

### **8.8.1. Below the Quantification Level (BLQ) Values**

Plasma concentrations that are BLQ will be set to  $\frac{1}{2} \times \text{BLQ}$ .

### **8.8.2. VAP-1/SSAO Activity Levels and Methylamine Concentration Time Data**

Individual plasma VAP-1/SSAO activity levels and methylamine concentration data will be listed separately for trough timepoints (PD Analysis Set) and trough and intensive timepoints (PK/PD Substudy Analysis Set). VAP-1/SSAO activity levels and methylamine concentrations will be summarized by nominal sampling time point and treatment group with descriptive statistics (number of non-missing observations, arithmetic mean, SD, median, Q1, Q3, minimum, maximum, geometric mean and geometric coefficient of variation [CV%]). The number of values BLQ will be presented for all patients and separately for PK/PD substudy patients.

The following rules will be applied in the presentation of plasma VAP-1/SSAO activity levels and methylamine concentration data if there are values that are BLQ or if there are missing values (e.g., no result [NR]) in a data series to be summarized.

- For the calculation of summary statistics, BLQ values will be set to  $\frac{1}{2} \times \text{BLQ}$ .
- Where there is NR, these will be set to missing.
- If there are less than three values in the data series, only the minimum, maximum and number of observations will be presented. The other summary statistics will be denoted as not calculated (NC). BLQ is considered a value.
- If all the values are BLQ, then the arithmetic mean, arithmetic SD, median, minimum and maximum will be presented as  $\frac{1}{2} \times \text{BLQ}$ , and the geometric mean and geometric CV% will be denoted as NC.

Individual patient, arithmetic mean VAP-1/SSAO activity levels and methylamine concentration-time profiles, for each TERN-201 dose, will be presented graphically on linear and logarithmic

scales separately for trough timepoints (PD Analysis Set) and trough and intensive timepoints (PK/PD Substudy Analysis Set) patients for Week 0/Day 1, Week 6, and Week 12. A reference line for LLOQ will be included on graphs.

VAP-1/SSAO activity levels and methylamine concentration data in listings will be presented to the same number of significant figures as provided by the analytical laboratory. Descriptive statistics will be displayed according to the rules outlined in [Section 4.1](#).

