### 8.7.3. Concentration-Time Data

Individual plasma TERN-201 and metabolite (TRN-001021 and TRN-001744) concentration data will be listed separately for trough concentrations (PK Analysis Set) and trough and intensive concentrations (PK/PD Substudy Analysis Set). Concentrations will be summarized by nominal sampling time point and treatment with descriptive statistics (number of non-missing observations, arithmetic mean, arithmetic SD, arithmetic coefficient of variation [CV%], median, Q1, Q3, minimum, maximum, geometric mean and geometric CV%). The number of values below quantification limit (BLQ) will be presented for all patients and separately for PK/PD substudy patients. Individual urine TERN-201 and metabolite (TRN-001021 and TRN-001744) concentrations and sample volume will be listed for each patient.

The following rules will be applied in the presentation of plasma concentration data if there are values that are BLQ or if there are missing values (e.g., no result [NR]) in a plasma concentration data series to be summarized.

- For the calculation of summary statistics, BLQ values will be set to zero.
- For the calculation of PK parameters, BLQ values will be set to zero prior to the first measurable concentration and set to missing after a measurable concentration is observed.
- If an embedded BLQ value is considered anomalous within the concentration time profile, this value will be excluded from the summary statistics.
- Where there is NR, these will be set to missing.
- If there are less than three values in the data series, only the minimum, maximum and number of observations will be presented. The other summary statistics will be denoted as not calculated (NC). BLQ is considered a value.
- If all the values are BLQ, then the arithmetic mean, arithmetic SD, median, minimum and maximum will be presented as zero, and the geometric mean and geometric CV% will be denoted as NC.
- If the value of the arithmetic mean or median is below the lower limit of quantification, these values will be presented as zero and the geometric mean and geometric CV% will be denoted as NC.

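### SAP 8.8.2 has the SD of an all-BLQ PD cell printed as half the LLOQ, although its own substitution rule makes that SD 0; the error is limited to the descriptive tables of PD levels

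*SAP*

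**What the plan says.** Three rules in the SAP bear on this.

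- **Substitution.** SAP 8.8.1 states for PD data: "Plasma concentrations that are BLQ will be set to" ½ × BLQ. SAP 8.8.2 repeats it for the tables: "For the calculation of summary statistics, BLQ values will be set to" ½ × BLQ.
- **All-BLQ cell.** The last bullet of the same list in 8.8.2 covers a cell in which nothing is quantifiable. It names the mean first and goes on: "arithmetic SD, median, minimum and maximum will be presented as". The value given there is again ½ × BLQ, so the SD receives the same number as the mean. For the two geometric statistics the bullet asks for NC instead.
- **Small cells.** "If there are less than three values in the data series, only the minimum, maximum and number of observations will be presented"; a BLQ result counts as a value. An SD is therefore shown from three values upwards.

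The parallel PK rule in SAP 8.7.3 substitutes zero, and for an all-BLQ series it says "then the arithmetic mean, arithmetic SD, median, minimum and maximum will be presented as zero".

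SAP 8.8.2 applies to both plasma VAP-1/SSAO activity and methylamine. It also asks for a count of BLQ results. SAP section 11, which lists changes from the protocol analyses, does not mention the point.

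**The concern.** The substitution rule and the all-BLQ rule sit in the same bullet list and cannot both be followed by calculation. Once every BLQ result has been set to the same number, the cell has no spread, yet the plan orders a positive SD. A programmer who lets the software compute the SD gets 0 and departs from the SAP. One who follows the SAP must hard-code a number that the data do not give.

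The PK list has the same structure and is right, because there the substituted value, the mean and the SD are all zero. The PD list may be that text with zero exchanged for ½ × BLQ. That is an inference about drafting, and the error does not depend on it.

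All-BLQ cells are plausible for VAP-1/SSAO activity on active drug: Protocol 4.3 cites more than 90% suppression at 10 mg in healthy participants. At stake is one wrong statistic in a planned table of PD levels.

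**Working it through.** **Inputs**

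- L = LLOQ. The documents do not give it, so results are in units of L.
- Substituted value: 0.5L (SAP 8.8.1 and 8.8.2). Reading ½ × BLQ as half the LLOQ is an inference, but it is the only reading that yields a number.
- Smallest cell that shows an SD: n = 3 (SAP 8.8.2).
- Planned cell sizes (SAP 2.2): about 8 on TERN-201 in the Part 1 sub-study, about 6 per dose level in the Part 2 sub-study, and about 20 per dose group for trough samples.

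**Step 1. The plan's figure.** In an all-BLQ cell the rule prints SD = 0.50L. It is prescribed, and no calculation on the substituted data reproduces it.

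**Step 2. The SD of the same cell.** s = √[Σ(x − x̄)² / (n − 1)]. Every x = 0.5L, so x̄ = 0.5L, each deviation is 0 and s = 0. This holds for every n, and also with divisor n.

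**Step 3. The PK parallel.** Every x = 0, so x̄ = 0 and s = 0, which agrees with SAP 8.7.3.

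**Step 4. One measurable value.** Take n = 8, with seven values at 0.5L and one at L; the all-BLQ bullet no longer applies.

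- x̄ = (7 × 0.5L + L)/8 = 0.5625L
- Σ(x − x̄)² = 7 × (0.0625L)² + (0.4375L)² = 0.0273L² + 0.1914L² = 0.2188L²
- s = √(0.2188L²/7) = 0.177L

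For one value v among n − 1 values at 0.5L, the formula reduces to s = (v − 0.5L)/√n. With v = L:

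| n | SD printed by the rule, all BLQ | SD computed, all BLQ | SD computed, one value at LLOQ, rest BLQ |
|---|---|---|---|
| 3 | 0.50L | 0 | 0.29L |
| 6 | 0.50L | 0 | 0.20L |
| 8 | 0.50L | 0 | 0.18L |
| 20 | 0.50L | 0 | 0.11L |

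The printed spread thus falls when variation first appears. For n = 8 the reversal lasts until the single measurable value reaches v = 0.5L + 0.5L√8 = 1.91L.

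**Step 5. Percent change.** A patient with baseline B whose post-dose value is BLQ has percent change 100 × (0.5L − B)/B. This differs between patients as B differs. SAP 8.8.3 has no presentation override for it, so its SD is computed in the usual way.

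**The case against.** The best defence is that the rest of the row limits the harm. Mean, median, minimum and maximum would all show the same number, and the quartiles would compute to it too. The geometric statistics would read NC, and the number of BLQ results is reported. Equal minimum and maximum tell a careful reader that the tabulated values do not vary. This stands, and it is the main reason for the low severity.

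One could also say that half the LLOQ is a sensible stand-in for unknown spread. True values between 0 and L can have an SD as large as √(8 × 0.25L²/7) = 0.53L for n = 8, with half of them at each end. But the SAP does not present the figure as a bound, and a bound should not be printed as an SD. The argument does show that 0 reflects the substitution and not proven uniformity, so NC is equally acceptable.

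A reader might infer more than the documents support:

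- *False error bars in the figures.* The profile plots in 8.8.2 are individual and arithmetic mean curves, with no SD bars named. The PD figures with bars in 8.8.3 show LS mean ± SE from the ANCOVA.
- *A printed CV of 100%.* SAP 8.8.2 plans no arithmetic CV for PD levels, and the geometric CV is NC in this case. The 100% arises only if a reader divides SD by mean.
- *A distorted secondary endpoint.* That endpoint is percent change in VAP-1/SSAO activity, handled in 8.8.3 (Step 5). The ANCOVA uses the patient values, not the printed SD.
- *The strongest drug effect always hit.* This fits VAP-1/SSAO activity only. Methylamine rises under inhibition (Protocol 2.2.2), so an all-BLQ methylamine cell would not signal strong suppression.
- *A wrong geometric mean.* It could be computed as 0.5L, but showing NC for a wholly imputed cell is a presentation choice.

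**Conclusion.** Wrong as written, at the lowest severity. In any all-BLQ cell of three or more values, SAP 8.8.2 prescribes an SD of 0.50 × LLOQ where its own substitution rule gives 0. The error is confined to the SD in the descriptive tables of VAP-1/SSAO activity and methylamine levels. The percent-change endpoint, ANCOVA estimates, confidence intervals and LS mean ± SE figures are unaffected.

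The conclusion rests on reading ½ × BLQ as half the LLOQ. How often the rule would apply cannot be determined. Without the LLOQ, the number of affected cells could be none (residual activity well above it) or most post-dose cells on active drug (residual activity below it). Suppression of more than 90% in healthy participants, measured with an exploratory assay (Protocol 2.2.2), does not by itself place every patient in a cell below the LLOQ.

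**What to change.** In the all-BLQ bullet of SAP 8.8.2, remove the arithmetic SD from the list of statistics presented as ½ × BLQ, and state that it is presented as 0 or as NC. Choose one of the two and use it throughout. The other entries in that bullet can stay. The cost is one sentence in the SAP and the matching table shell; no new data and no change to any model are needed.

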### 8.8.3. Change from Baseline

Descriptive statistics of VAP-1/SSAO activity and methylamine values, change from baseline, and percent change from baseline values will be presented by treatment group for each visit separately using the PD Analysis Set for trough timepoints and using the PK/PD Analysis Set for trough and intensive timepoints. Baseline is defined as the Week 0/Day 1 pre-dose value.

Analyses of change (and separately percent change) from baseline will be carried out using an ANCOVA model at time point with change (and separately percent change) from baseline as the dependent variable including treatment group and randomization strata as fixed effects and baseline as a covariate.

The estimates of least-square (LS) means, standard errors (SE), and 90% and 95% CIs will be presented by treatment group. Estimates of the LS mean difference for each pairwise comparison will be presented with associated the standard error of the difference, and 90% and 95% CIs of the difference.

Figures of LS mean ( $\pm$ SE) change from baseline, and percent change from the ANCOVA model will be presented over time by treatment group.

Analyses to explore the correlation of plasma VAP-1/SSAO activity and methylamine changes with liver function tests, LFC, cT1, and other biomarker changes may be evaluated.

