Plasma exposures to TERN-201 were greater than dose proportional. TERN-201 was rapidly cleared from plasma. Steady state was achieved in the highest dose group (10 mg) after Day 7 of dosing. The half-life of TERN-201 increased with dose, suggesting saturable, target-mediated clearance.

Single and multiple doses of TERN-201 significantly suppressed plasma total amine oxidase activity at all doses studied. Using an exploratory assay to assess the effect of TERN-201 on VAP-1/SSAO-specific amine oxidase activity in the plasma, near complete inhibition (>80% with 1 mg, > 90% with 10 mg) was observed after only a single dose on Day 1 (achieved within 4 hours after dosing) with sustained suppression over the dosing period in MAD cohorts. Dose-dependent increases in methylamine, an endogenous substrate of VAP-1/SSAO predicted to increase upon VAP-1/SSAO inhibition, were observed after the first dose of TERN-201 and continued to increase in a dose-dependent manner after multiple doses of TERN-201.

Based on the exploratory assessment on plasma PK of two TERN-201 metabolites, TRN-001021 and TRN-001744, the percentages of either metabolite AUC relative to the total TERN-201-related plasma AUC (sum of TERN-201, TRN-001021, and TRN-001744) were calculated. Median TRN-001021 AUC was <10% and 13.7% of the total plasma AUC associated with TERN-201 in the 4 mg and 10 mg groups, respectively. Median TRN-001744 AUC was 11.5% and <10% of the total plasma AUC associated with TERN-201 in the 4 mg and 10 mg groups, respectively.

Additional details on Study TERN201-US-A101 are available in the Investigator's Brochure.

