4.3. Justification for Dose

Doses for this study were based on results from the FIH Phase 1 study, TERN201-US-A101, which evaluated 4 SAD cohorts of TERN-201 or matching placebo at 1 mg, 3 mg, 6 mg, or 10 mg, and 3 MAD cohorts of TERN-201 or matching placebo at 1 mg for 7 days, 4 mg for 7 days, or 10 mg for 14 days.

In the FIH study, single or multiple doses of TERN-201 resulted in rapid inhibition of plasma amine oxidase activity, with sustained inhibition during 14 days of dosing. TERN-201 demonstrated a favorable safety profile and was overall well-tolerated at all doses studied (Section 2.2.2).

Part 1 of this study assesses 10 mg of TERN-201, the highest dose studied in the FIH study. In the FIH study, this dose led to >90% suppression of plasma VAP-1/SSAO-specific amine oxidase activity in healthy participants. NASH patients are expected to have a higher baseline level of VAP-1, and thus the PD effect of TERN-201 in NASH patients may differ from healthy participants. A higher dose of up to 20 mg may be enrolled based on assessment of safety and PK with the 10 mg dose, and a lower dose of 4 mg may be enrolled based on observation of a robust PD effect of TERN-201 on plasma VAP-1/SSAO activity in the 10 mg cohort, thus minimizing the number of patients exposed until the PK and PD effects of TERN-201 can be confirmed in Part 1 of the study.

Toxicity and safety pharmacology studies support starting with the 10 mg dose and enrolling a higher dose up to 20 mg.

Additional details on available data from Study TERN201-US-A101 are provided in the TERN-201 Investigator's Brochure.

5. Study Population

Prospective approval of protocol deviations to recruitment and enrollment criteria, also known as protocol waivers or exemptions, is not permitted.

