9.4.3.2. Change from Baseline in Plasma VAP-1/SSAO Activity

A secondary efficacy endpoint is change from baseline in plasma VAP-1/SSAO activity with 12 weeks of treatment in patients treated with either TERN-201 or matching placebo. The change and percent change from baseline in plasma VAP-1/SSAO amine oxidase activity in each TERN-201 group will be compared with placebo separately at each post baseline visit, without controlling for any family-wise error rate (overall type I error), using MMRM (mixed model repeated measures) model with treatment group, visit, and treatment group by visit interaction as factors and baseline value as covariate.

Change and percent change from baseline plasma VAP-1/SSAO amine oxidase activity will be listed and summarized with descriptive statistics including arithmetic and geometric mean, median, standard deviation, arithmetic and geometric CV, minimum, and maximum. Exposure-response and dose-response relationships of orally administered TERN-201 will also be assessed as applicable (exploratory endpoints).

Exposure-response and dose-response analysis may be produced if Part 2 of the study is enrolled, as applicable. The change and percent change from baseline in plasma VAP-1/SSAO activity will be compared between the different TERN-201 dose groups and placebo using an analysis of covariance (ANCOVA) model with the treatment group as a factor and baseline values as a covariate. Corresponding least square mean treatment differences with 2 sided 95% confidence limits will be computed for each pairwise comparison.

Further details on the analysis models will be provided in the SAP.

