#### 4.4. Data Conventions

The precision of original measurements will be maintained in summaries, when possible.

Quantitative safety laboratory tests containing less than (<) and greater than (>) symbols are test results that are below and above quantifiable limits, respectively. In order to retain these values for analysis purpose, the following will be imputed and stored within the analysis datasets:

- For values with <, the imputed value will be the numeric portion  $\times 0.9$ .
- For values with >, the imputed value will be the numeric portion  $\times 1.1$ .

PK and PD imputation of values below the limitation of quantitation (BLQ) are specified in [Section 8.7.1](#) and [Section 8.8.1](#), respectively.

Variables with a non-normal distribution that impacts the interpretation or validity of the planned analysis may have a data transformation applied (e.g., ln,  $\log_{10}$ ).

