## **8.6. Multiple Comparisons/Multiplicity**

There will be no adjustment for multiplicity. Statistical testing will be considered nominal, descriptive and exploratory.

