#### **8.8.4.1. PD Parameter Data Handling**

#### **8.8.4.2. Calculation of AUC**

AUCs will be calculated using linear trapezoidal rule. For any partial AUC determination (i.e., AUC over a dosing interval), nominal time will generally be used for the end of the interval.

The minimum requirement for the calculation of AUC will be the inclusion of at least three consecutive plasma VAP-1/SSAO activity or methylamine concentrations above the LLOQ.

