#### 8.8.4.4. Dose Response

If Part 2 enrolls, dose-response may be evaluated, if the data warrants, based on the pairwise comparisons of pre-dose/trough values for plasma VAP-1/SSAO activity ( $A_{avg}$  and  $A_{min}$ ) and methylamine concentration ( $C_{avg}$  and  $C_{max}$ ) from the ANCOVA models specified above (Section 8.8.4.3). In addition, pre-dose/trough VAP-1/SSAO activity ( $A_{avg}$  and  $A_{min}$ ) and methylamine concentration ( $C_{avg}$  and  $C_{max}$ ) will also be plotted by treatment group based on values, change from baseline, and percent change from baseline.

Dose response will also be evaluated using a REML based MMRM. The dependent variable will be the percent change (separately for change) from baseline for plasma VAP-1/SSAO activity and methylamine. The model will include the following fixed effects:

- Treatment group (4 levels: placebo [0 mg], 4 mg, 10 mg, 20 mg)
- Categorical time
- Treatment group by time interaction
- Baseline value

An unstructured covariance model will be used. If the computational algorithm fails to converge, the following structures will be executed: heterogeneous Toeplitz, heterogeneous First-Order Autoregressive [AR (1)], heterogeneous compound symmetry (HCS), Toeplitz, AR(1), and compound symmetry (CS). The covariance structure converging to the best fit, as determined by Akaike's information criterion (AIC, the smaller the AIC value the better the model fit), will be used. If the model converges with an unstructured covariance matrix, the Kenward and Roger method will be used to calculate the denominator degrees of freedom for the test of fixed effects. If a structured covariance is used, then a robust sandwich estimator will be utilized for estimating the variance of the treatment effect estimate.

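### The AUC rule for VAP-1/SSAO activity can drop the most suppressed sub-study profiles; secondarily, SAP 8.8.3 makes no provision for unequal variance between drug and placebo

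*SAP*

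**What the plan says.** **AUC rule.** SAP 8.8.4 computes plasma PD parameters in PK/PD sub-study patients only: about 6 to 8 per TERN-201 dose (SAP 2.2 gives 8 in Part 1 and 6 per dose in Part 2; Protocol 6.4 gives 6 in Part 1). For an AUC, 8.8.4.2 requires "the inclusion of at least three consecutive plasma VAP-1/SSAO activity or methylamine concentrations above the LLOQ". Section 8.8.4.3 sets uncalculated parameters to missing in the summaries. Section 8.8.1 already gives a below-limit PD result half the limit, and 8.8.2 uses that value in the summaries by time point.

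**Variance.** SAP 8.8.3 compares arms at each time point "using an ANCOVA model at time point with change (and separately percent change) from baseline as the dependent variable including treatment group", plus randomization stratum and baseline, and reports every pairwise difference with 90% and 95% intervals. It names no variance check, arm-specific variance or robust standard error. The nearest general safeguard is SAP 4.4: "Variables with a non-normal distribution that impacts the interpretation or validity of the planned analysis may have a data transformation applied". Part 1 has 20 drug and 10 placebo patients and is analysed after it completes (SAP 8.3). If Part 2 enrolls, placebo is pooled (SAP 4.6), giving up to four groups of about 20. SAP 8.6 adds: "Statistical testing will be considered nominal, descriptive and exploratory".

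**The concern.** For a drug concentration, a profile without three successive quantifiable values carries little information. For the activity of an inhibited enzyme it may be the best response in the study. A rule that excludes it selects on outcome, and selects harder at more suppressive doses. At Weeks 6 and 12, when the whole profile may be suppressed, the AAUCtau summary could show less suppression than was achieved and flatten the difference between doses. The exposure-response work in SAP 8.9 models activity PD parameters without naming which, so it could inherit the problem if AAUCtau is used. Methylamine rises with inhibition, so the argument does not apply to it.

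The variance question starts from the first-in-human study, where "near complete inhibition (>80% with 1 mg, > 90% with 10 mg) was observed after only a single dose on Day 1" in healthy participants. Percent change cannot go below −100%. Drug arms pressed against that floor would have little spread while placebo keeps its own. One pooled residual variance would then be too small for drug-placebo differences and too large for dose-dose differences.

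**Working it through.** The documents give no LLOQ, no SDs and no power calculation for this endpoint, so there is no plan figure to reproduce. All spreads and limits below are assumptions.

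**1. AUC rule**

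Activity as a percentage of baseline is taken as lognormal around a median m. Between-patient CV is 50%, within-patient CV 25%, with the eight samples from pre-dose to 24 h.

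- Log SDs: √ln(1 + 0.5²) = 0.472 and √ln(1 + 0.25²) = 0.246.
- True mean: m × √(1.25 × 1.0625) = 1.152m, so medians of 8, 5 and 2% give means of 9.2, 5.8 and 2.3%.
- LLOQ is set at 5% of baseline, with 200,000 simulated profiles per setting.

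| Dose (assumed median residual) | Calculable | Expected patients | Mean, calculable only | True mean | Mean, half-LLOQ on all |
|---|---|---|---|---|---|
| 4 mg (8%) | 82% | 4.9 of 6 | 10.2% | 9.2% | 9.0% |
| 10 mg (5%) | 48% | 3.8 of 8 | 7.7% | 5.8% | 5.3% |
| 20 mg (2%) | 3% | 0.2 of 6 | 5.7% | 2.3% | 2.7% |

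The gap between the 4 and 20 mg means shrinks from 9.2 − 2.3 = 6.9 points to 10.2 − 5.7 = 4.5.

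Range: at a median residual of 15% and LLOQ up to 5%, fewer than 2% of profiles are lost. At LLOQ 10% and a median of 2%, half-LLOQ gives 5.0% against a true 2.3%, so imputation also understates suppression; the present rule would leave no profile at all in over 99% of eight-patient groups. Over 20 combinations of median (1 to 15%) and LLOQ (1 to 10%), half-LLOQ on all profiles was at least as close to the truth as the calculable profiles wherever any were kept.

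**2. Common variance in 8.8.3**

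Ratio of model SE to true SE, with SDp for placebo and SDd for drug:

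- Part 1: √[(9·SDp² + 19·SDd²)/28] × √(1/10 + 1/20) ÷ √(SDp²/10 + SDd²/20)
- Four arms of 20: √[(SDp² + 3·SDd²)/4] × √(1/20 + 1/20) ÷ √(SDp²/20 + SDd²/20)
- Dose-dose, four arms: √[(SDp² + 3·SDd²)/4] ÷ SDd

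With SDp = 15 and SDd = 3 points:

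- Part 1: √78.43 × 0.387 = 3.43 against √22.95 = 4.79, ratio 0.72.
- Four arms: √63 × 0.316 = 2.51 against √11.7 = 3.42, ratio 0.73.
- Dose-dose: 7.94/3 = 2.65, so too wide.

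Simulated coverage of nominal 95% drug-placebo intervals under uniform suppression:

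| SDp/SDd | Part 1 SE ratio | Part 1 coverage | Four-arm SE ratio | Four-arm coverage |
|---|---|---|---|---|
| 2 | 0.81 | 89.0% | 0.84 | 90.4% |
| 3 | 0.75 | 85.9% | 0.78 | 87.3% |
| 5 | 0.72 | 83.3% | 0.73 | 85.0% |
| 10 | 0.70 | 81.8% | 0.71 | 83.1% |

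If some drug patients are not suppressed, the drug arms gain spread. With SDp 10–25 and SDd 2–5, Part 1 coverage is 82–90% at 5% unsuppressed and 89–93% at 10%; in four arms it is already 92–95% at 5%.

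With one variance for placebo and one for the TERN-201 arms, coverage under uniform suppression is 94–96% in both designs. In Part 1 it is 90–95% at 5% unsuppressed and 89–95% at 10%.

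**The case against.** **On the AUC rule.** AAUCtau enters neither the ANCOVA of 8.8.4.3 nor the dose-response analysis of 8.8.4.4; both name A_avg and A_min. Table 8 defines A_avg as an observed average and does not say that it comes from an AUC. So a reader might infer that the rule distorts the secondary endpoint or the planned dose-response tests, but the documents do not support that. Nor does the rule contradict 8.8.1: one section assigns a value, the other sets eligibility for one parameter. Below-limit counts (8.8.2) and non-missing n (8.8.4.3) would reveal the loss. Protocol 4.3 expects higher baseline VAP-1 in NASH; if activity is higher too, a fixed LLOQ is a smaller share of baseline. All of this stands and limits the reach of the point. It does not correct the mean of the profiles that remain.

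**On variance.** The premise is conditional. The inhibition figure comes from healthy participants with an exploratory assay, and Protocol 4.3 says "the PD effect of TERN-201 in NASH patients may differ from healthy participants". At 30% residual activity, Part 1 coverage is 89–96%; if placebo SD were half the drug SD, intervals would be too wide (97.7%). On a log-ratio scale, which 4.4 permits, the inequality reverses and coverage is 95–99% under uniform suppression. That transformation is optional, however, and triggered by non-normality rather than unequal spread. No decision is tied to these intervals: the Part 2 criteria in SAP 8.3 name none, and an effect near −90 points stays clear of zero at any width considered here.

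It is also tempting to think the shortfall is mainly a Part 1 problem, cured when pooled placebo reaches 20. It is not: 8.8.3 has one treatment factor, so the residual variance is averaged over placebo and up to three low-variance drug arms. Under uniform suppression the four-arm shortfall is almost as large. Only separate two-arm models of 20 against 20 would remove it (coverage 94.0–95.1%).

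**Conclusion.** The AUC point holds on the text alone: the rule can exclude profiles because the drug worked. Its certain effect is confined to the AAUCtau summary in about 6 to 8 sub-study patients per dose, with a possible effect on SAP 8.9 if AAUCtau is modelled there. A_min and the trough-based secondary endpoint are untouched, and A_avg is affected only if it is derived from AUC. The size depends on an LLOQ that the documents do not give: negligible if well below residual activity, large if near or above it.

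The variance point is real but secondary. If suppression is near complete and uniform and placebo varies more than drug, nominal 95% drug-placebo intervals cover about 82–90% in both designs, and dose-dose intervals are too wide. With some drug patients unsuppressed, the shortfall nearly disappears in four arms at about 5%; in Part 1 it eases clearly only nearer 10%. A reader might infer a risk of a false drug effect; the documents do not support that. Only stated precision is affected, in results that the SAP calls nominal. Nothing here is a finding against the repeated-measures model in 8.8.4.4, which was not assessed.

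Both changes are worth making because they are cheap. Neither alters the study's main conclusions.

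**What to change.** **SAP 8.8.4.2.** For VAP-1/SSAO activity, drop the above-LLOQ minimum and calculate AAUCtau with below-limit values at half LLOQ, as in 8.8.1. Report the number of imputed values and affected profiles by arm. State the limit: when residual activity is far below LLOQ, half-LLOQ overstates it, though less than excluding those profiles does.

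**SAP 8.8.3.** Allow one residual variance for placebo and one for the TERN-201 arms, with Satterthwaite or Kenward-Roger degrees of freedom. Keep the common-variance ANCOVA as a sensitivity analysis.

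**Cost.** One model option and a few SAP sentences; no new data. The split leaves fewer effective degrees of freedom, chiefly at intensive time points, where placebo rests on about 4 patients in Part 1 or 7 over both parts. It gives little gain at the low end of coverage when about 10% of drug patients are unsuppressed. If spread falls with dose, dose-dose intervals can become slightly narrow: 4 versus 20 mg coverage of 91–94%, against 96–100% with the common variance. The SAP should say so.
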